7.6 Determination of Sample Size

The sample size for this study was determined from results of two previous studies. The first was a study in subjects with acute upper back, neck, or shoulder spasm and pain, which showed a difference of 0.4 in the average of Day 1 through Day 7 between the placebo and active groups, and standard deviations (SDs) between 1.76 and 1.93 (across placebo and active groups respectively; [Collaku, 2017](#)). A sample size of 400 subjects (80 per group) would provide at least 80% power to detect a difference of 0.9 between the placebo and treatment groups in the NRS scale, assuming a two-sample t-test at the 5% level of significance and a pooled SD of 2.0. This sample size assumes an effect size of 0.45 ($0.9/2.0 = 0.45$, using the formula $\text{Effect Size} = \text{Mean}/\text{SD}$), which is larger than that seen in the reference study but consistent with that seen in a second study.

A second previous study in subjects with acute musculoskeletal spasm associated with low back pain showed effect sizes ranging from 0.57 to 0.62 for lumbar cinesalgia, based on a treatment difference of 9.6 at Day 3, with SDs of 15.5 (treated group) and 16.7 (placebo group) (Chandanwale, 2011). This study demonstrated effect sizes ranging from 1.1 to 1.6, based on a difference of 24.2 at Day 14 with SDs of 15.1 (treated group) and 23.0 (placebo group). The effect size of the current study is expected to be similar to that in Chandanwale, though sample size estimates have been made more conservative to provide sufficient power to detect smaller differences. Though the primary comparison of interest in this study is Day 14, the study is sufficiently powered to detect a treatment difference at Day 4 based on effect sizes ranging from 0.35 to 0.45.

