9.3. Withdrawal Criteria

Subjects will be advised that they are free to withdraw from the study at any time. Reasons that subjects may discontinue or be withdrawn from the study may include, but are not limited to:

- AEs
- Subject request
- Investigator decision
- Protocol non-compliance
- Study termination by the Sponsor or Institutional Review Board (IRB).

If a subject is withdrawn from the study, all efforts will be made to complete the Visit 3 (EOT) procedures at an Early Termination visit (see [Section 11.2.4](#)). All information, including the reason for withdrawal, should be reported on the applicable pages of the electronic case report form (eCRF).

For subjects who are lost to follow-up, three documented attempts will be made to contact the subject for follow-up information, including reason for discontinuation and follow-up of AEs. Subjects who withdraw from the study will not be replaced.

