17.2. Determination of Sample Size

The sample size for this study was determined from results of two previous studies. The first was a study in subjects with acute upper back, neck, or shoulder spasm and pain, which showed a difference of 0.4 in the average of Day 1 through Day 7 between the placebo and active groups, and SDs between 1.76 and 1.93 (across placebo and active groups respectively) (Collaku, 2017). A sample size of 400 subjects (80 per group) would provide at least 80% power to detect a difference of 0.9 between the placebo and treatment groups in the NRS scale, assuming a two-sample t-test at the 5% level of significance and a pooled SD of 2.0. This sample size assumes an effect size of 0.45 ($0.9/2.0 = 0.45$), using the formula $\text{Effect Size} = \text{Mean}/\text{SD}$, which is larger than that seen in the reference study but consistent with that seen in a second study.

A second previous study in subjects with acute musculoskeletal spasm associated with back pain showed effect sizes ranging from 0.57 to 0.62 for lumbar cinelgasia, based on a treatment difference of 9.6 at Day 3, with SDs of 15.5 (treated group) and 16.7 (placebo group) (Chandanwale, 2011). This study demonstrated effect sizes ranging from 1.1 to 1.6, based on a difference of 24.2 at Day 14 with SDs of 15.1 (treated group) and 23.0 (placebo group). The effect size of the current study is expected to be similar to that in Chandanwale, though sample size estimates have been made more conservative to provide sufficient power to detect smaller differences. Though the primary comparison of interest in this study is Day 14, the study is sufficiently powered to detect a treatment difference at Day 4 based on effect sizes ranging from 0.35 to 0.45.

The power for this range of effect sizes across six different scenarios for a test of linear trend, as well as a comparison between the high dose and placebo only, is provided below, assuming $n=80$ in each group. Assuming an effect size of 0.4 (averaging the lowest and highest effects sizes)

yields power estimates that are greater than 80% for each scenario tested, except when all treatment groups have identical differences from placebo.

Sample size considerations are provided in [Table 1](#).

Table 1 Sample Size Considerations

Effect Size (High Dose vs. Placebo)	Hypothesized Difference from Placebo				Power: Linear Contrast	Power: High Dose vs. Placebo
	Dose Group 1	Dose Group 2	Dose Group 3	Dose Group 4		

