7.4.4 Primary Efficacy Endpoint Analysis Methods

The primary efficacy endpoint is NRS subject-rated pain “right now” due to acute back spasm on Day 14 for all subjects in the ITT population. This analysis will be performed using a linear test of trend across all tolperisone doses.

The null and alternate hypotheses to be tested are:

H₀: There is no significant trend in NRS rating of pain “right now” across dose groups

H₁: There is significant trend in NRS rating of pain “right now” across dose groups

The linear test of trend will be performed using a mixed effect model for repeated measures (MMRM) using an unstructured covariance matrix to model within-patient errors. However, if the computational algorithm fails to converge, other covariance structures will be evaluated (e.g., compound symmetry). The covariance structure converging to the best fit, as determined by Akaike’s information criterion, will be used. The Kenward and Roger method will be used to calculate the denominator degrees of freedom for the test of fixed effects. Based on this model, the hypothesis test described above will be tested using a two-sided test at the $\alpha=0.05$ level of significance.

The response variable will be the observed NRS rating of pain “right now”. The observed value on Day 14 is the primary time point of interest. The model will include factors for treatment group (5 levels: placebo, 150 mg/day, 300 mg/day, 450 mg/day and 600 mg/day) and visit (three levels: Day 1/Baseline, Day 4, and Day 14) as fixed effects, the treatment by visit interaction, and the baseline NRS rating as a covariate. The primary analysis will be based on all available data without imputation. Day 14 will reflect subjects that have completed the scheduled Day 14 (Visit 3). Subjects discontinuing the study may be analyzed as part of the sensitivity analysis using data imputation methods (LOCF and Multiple Imputation) to address missing data.

The observed NRS rating and change from baseline values will be presented using descriptive statistics for each treatment group by visit. The p-value for the overall test of trend on Day 14 will be presented. The pairwise least-square mean (LSM) estimates and least-square mean differences (LSMD) for each tolperisone dose level versus placebo will also be presented with 95% confidence intervals of the LSMD and associated p-values for the Day 14 visit observed values.

A plot of NRS subject rating of pain right now across study days will be presented.

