7.7.2 Other Changes

An independent audit of Site 21 ([name]), conducted May 12 and May 15, 2019, described substantial evidence of clinical trial misconduct during the execution of the trial. Based on the inspection findings report (signed May 17, 2019), Site 21 subject data will be excluded from all analyses described in this SAP.

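### The stated power of at least 80% holds only with the full 80 analysed per arm; neither document allows for loss, and SAP 7.6 was not updated when SAP 7.7.2 excluded Site 21.

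*SAP*

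**What the plan says.** SAP 7.6, like the synopsis and Protocol 17.2, states: "A sample size of 400 subjects (80 per group) would provide at least 80% power to detect a difference of 0.9". The conditions are given as "assuming a two-sample t-test at the 5% level of significance and a pooled SD of 2.0", and "This sample size assumes an effect size of 0.45". Protocol 17.2 then gives Table 1, with power for the linear trend and for high dose versus placebo at 80 in each group. It says that an effect size of 0.40 "yields power estimates that are greater than 80% for each scenario tested, except when all treatment groups have identical differences from placebo". None of these sections adds an allowance for dropout.

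Four other places bear on the number analysed:

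- Protocol 9.3: "Subjects who withdraw from the study will not be replaced".
- SAP 7.4.4: the primary analysis is a mixed model for repeated measures (MMRM) without imputation, and "Day 14 will reflect subjects that have completed the scheduled Day 14 (Visit 3)".
- SAP 7.4.6.2: LOCF is used if dropout reaches 5% (20 of 400), and multiple imputation may be explored if it reaches 15% (60 of 400).
- SAP 7.7.2: after an audit, "Site 21 subject data will be excluded from all analyses described in this SAP".

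**The concern.** The power is quoted at the number randomised, with almost no slack, in a plan where fewer will supply a Day 14 value. One loss, Site 21, is already decided in the same SAP that repeats 400 and 80 per group. Protocol 11.2.3 adds another route to loss, because a positive drug or alcohol test on study ends participation.

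The trial is meant to pick a Phase 3 dose. If a dose-versus-placebo comparison, or a trend of one of the weaker shapes, comes out non-significant, readers will judge it against the stated power. That figure should be the one the analysed trial has.

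**Working it through.** **Inputs.** Difference 0.9, SD 2.0, so d = 0.9/2.0 = 0.45; two-sample t-test at 5%; 80 per group (SAP 7.6). Two-sided testing (SAP 7.1.1). Equal allocation to five arms (SAP 6.3.2). Trend shapes from Protocol Table 1. About 45 sites (SAP 6.1). Loss rates of 5%, 10% and 15% are assumptions; 5% and 15% are chosen because they are the SAP's imputation triggers.

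**Pairwise comparison.** Power comes from the non-central t distribution with df = 2n − 2 and non-centrality d·√(n/2).

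| n per arm | Non-centrality | Power |
|---|---|---|
| 80 | 0.45·√40 = 2.846 | 80.8% |
| 79 | 0.45·√39.5 = 2.828 | 80.3% |
| 78 | 0.45·√39 = 2.810 | 79.7% |
| 76 (5% loss) | 0.45·√38 = 2.774 | 78.7% |
| 72 (10% loss) | 0.45·√36 = 2.700 | 76.5% |
| 68 (15% loss) | 0.45·√34 = 2.624 | 74.1% |

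The first row reproduces the plan's figure (Table 1 prints 81%). The smallest n that reaches 80% is 79, so the margin is one per arm, or 5 of 400.

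**Linear trend.** With contrast (−2, −1, 0, 1, 2) over placebo and four doses, the squared coefficients sum to 10. The non-centrality is L·√(n/10) with df = 5n − 5, where L is the contrast of the means in SD units. For the shape 0.1, 0.2, 0.3, 0.4, L = −0.1 + 0.3 + 2(0.4) = 1.00, and at n = 80 the non-centrality is √8 = 2.828 and power 80.6%. Table 1 prints 81%.

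Shapes at effect size 0.40:

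| Shape (doses 1-4) | L | Table 1 | n = 80 | n = 76 | n = 68 |
|---|---|---|---|---|---|
| 0, 0, 0.2, 0.4 | 1.00 | 81% | 80.6% | 78.5% | 73.9% |
| 0.1, 0.2, 0.3, 0.4 | 1.00 | 81% | 80.6% | 78.5% | 73.9% |
| 0.05, 0.1, 0.26, 0.4 | 1.01 | 81% | 81.3% | 79.3% | 74.7% |
| 0, 0.13, 0.26, 0.4 | 1.06 | 85% | 84.9% | 83.0% | 78.7% |
| 0, 0.1, 0.3, 0.4 | 1.10 | 87% | 87.4% | 85.7% | 81.6% |
| 0, 0, 0.4, 0.4 | 1.20 | 92% | 92.3% | 91.0% | 87.7% |
| flat 0.4 | 0.80 | 62% | 61.7% | 59.5% | 54.8% |

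At 5% loss, the Protocol's sentence about power above 80% fails for three of the six graded shapes.

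At effect size 0.45, the six graded shapes give 88.5-96.8% at 80 per arm, 86.9-96.0% at 76 and 83.0-93.9% at 68. The flat shape gives 71.9%, 69.7% and 64.8%.

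**Site 21.** Its size is not in the documents. If it were an average site, it would hold 400/45 = 8.9 subjects, or 8.9/5 = 1.8 per arm. That leaves 78.2 per arm and pairwise power of 79.9%. With 5% dropout as well, n is 78.2 × 0.95 = 74.3 and power 77.8%.

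**What adjustment could recover.** A baseline covariate correlated r with the Day 14 rating multiplies the residual variance by 1 − r². It offsets a loss fraction f when r = √f: √0.05 = 0.22 and √0.15 = 0.39. The documents give no value for r.

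**The case against.** The strongest reply is that the plan contains no arithmetic error. It states its conditions, 80 per group and SD 2.0, and under them the figures are right. That stands: what is missing is an allowance for loss.

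Second, the pairwise t-test is not the primary test. The primary hypothesis is the linear trend, and at 0.45 every graded shape stays above 80% even after 15% loss. This also stands. A reader might infer that the primary test is underpowered generally, and Table 1 does not support that. The exposed parts are the pairwise comparisons, the three 0.40 shapes listed at 81%, and the flat shape, whose low power the Protocol already discloses.

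Third, the MMRM uses Day 4 ratings from subjects who drop out and adjusts for baseline, so an unadjusted calculation overstates the loss. It is therefore too strong to say that only completed Day 14 visits contribute. Likewise, with error pooled over five arms, 78 per arm gives 80.05%. However, the plan claims no such gain, and its power statement names an unadjusted two-sample test.

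Fourth, a reader might take 5% and 15% as the SAP's dropout forecasts. They are conditional triggers only.

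Fifth, a reader might argue that SD 2.0 is too small. The first cited study "showed a difference of 0.4 in the average of Day 1 through Day 7 between the placebo and active groups", with SDs of 1.76 to 1.93, whereas the endpoint here is a single rating. The documents do not confirm that those SDs belong to a seven-day mean, and they give no between-day correlation, so no figure can be built on this. The plan also rounded the SD up to 2.0 and took an effect size below the second study's 0.57 to 1.6.

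Finally, restating power changes no estimate or test, and the planned confidence intervals will show the precision achieved. That limits the importance of the point, but a decided exclusion should still not sit beside an unchanged power claim.

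**Conclusion.** The point holds in limited form. The two power statements are correct at 80 analysed per arm and have almost no margin below it. Pairwise, the shortfall is about 2 percentage points at 5% loss and under 7 at 15% (80.8% to 78.7% and 74.1%). The three weakest graded 0.40 trend shapes lose about as much.

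These sizes assume equal loss across arms, SD 2.0 and no covariate gain. Actual enrolment (the target is approximate), the dropout rate and the size of Site 21 are not given. An average-sized Site 21 alone would take pairwise power only just below 80%. This is worth correcting because one loss is already certain and the correction is cheap. It does not undermine the design.

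**What to change.** In SAP 7.6, before database lock and while still blinded:

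1. State the evaluable number per arm expected after the Site 21 exclusion and known dropout. If arm counts would risk the blind, use the overall count divided by five.
2. Replace the unconditional power claim with power at that number, both for the primary linear trend (all shapes in Protocol Table 1) and for the pairwise comparisons. Say that this supersedes the corresponding sentences in Protocol 17.2 and the synopsis.
3. Note that the figures are unadjusted, and that baseline adjustment and Day 4 data in the MMRM may recover part of the loss, using the correlations of about 0.22 and 0.39 derived above.

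The cost is a short text change and a slightly less favourable stated figure. Patients, design and analysis are unaffected.

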7.7 Changes in the Conduct of the Study or Planned Analyses

7.7.1 Changes in Planned Analyses

VAS ratings of sleepiness will be analyzed using an ANOVA in place of an ANCOVA model since no baseline values are collected to be used as a covariate. Daily activity scores and Subject Rating of Medication Helpfulness will be summarized categorically and the comparison of each group to placebo will be conducted using a Wilcoxon Rank Sum test for the Day 14 values instead of an MMRM or ANCOVA model.

7.7.2 Other Changes

An independent audit of Site 21 ([name]), conducted May 12 and May 15, 2019, described substantial evidence of clinical trial misconduct during the execution of the trial. Based on the inspection findings report (signed May 17, 2019), Site 21 subject data will be excluded from all analyses described in this SAP.

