The primary efficacy endpoint is subject-rated pain “right now” due to acute back spasm using an NRS (0-10) scale, from no pain to worst possible pain for the clinic visit on Day 14. This analysis will be performed using a linear test of trend across doses, using a mixed effect model for repeated measures. The model will include treatment and time as fixed effects, the treatment by time interaction, and the baseline NRS rating as a covariate. Differences in linear trend for each dose level versus placebo will be presented with 95% confidence intervals and associated p-values. The analysis performed for the primary endpoint will be repeated for the NRS at Day 4. Additional analyses for secondary efficacy endpoints will be conducted using repeated measures and analysis of covariance for continuous variables, a Wilcoxon Rank Sum test for categorical variables, and Kaplan-Meier analysis for time to pain relief.

Safety Analysis:

Safety measures will be summarized using descriptive statistics and listed for each subject.

Safety analysis will be based on all subjects randomized who receive at least 1 dose of the study medication. The safety analysis will evaluate AEs and additional safety parameters. The number and percentage of subjects experiencing at least one AE will be summarized by body system, preferred term, and treatment. If appropriate, AEs will also be summarized by intensity and relationship to study drug. Serious adverse events (SAEs), if any, will be tabulated.

Additional safety parameters will be assessed from summaries of physical examinations, 12-lead ECGs and vital signs. The 12-lead ECG results will be categorized as normal, clinically significant abnormal, and not clinically significant abnormal. Hematology, chemistry and urinalysis laboratory test results will be categorized relative to the normal ranges. The changes from baseline for each of these parameters from Screening to EOT will be presented. Complete listings and summary tables for all safety information including AEs, laboratory safety data, ECG, vital signs and physical examination will be included in the study report.

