17.4.3. Safety Analysis

Safety analysis will be based on all subjects randomized who receive at least one dose of the study drug. The safety analysis will evaluate adverse events and additional safety parameters.

Additional safety parameters will be assessed from summaries of physical examinations, 12-lead ECGs and vital signs.

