7.2 Analysis Populations

The analysis populations are defined as follows:

- **Intent-to-Treat (ITT) Population:** All randomized subjects who receive any amount of study drug. This population will be used as the primary analysis population for all efficacy endpoints. Subjects will be included in this population based on their randomized treatment assignment.
- **Safety Population:** All subjects who receive any amount of study drug. This population will be used for all summaries of safety data. Subjects will be included in this population based on the highest dose level received.
- **Per-Protocol (PP) Population:** All randomized subjects who complete the study treatment period with a minimum of 12 days of treatment and have no significant protocol violations that would affect the efficacy analyses. The PP Population will be determined prior to database lock and will be used for sensitivity analyses on the primary and select secondary endpoints. Subjects with major protocol deviations will be excluded from the efficacy analyses. See section 7.3.2 for further details on protocol deviations.

Data summaries to be presented on both the Safety Population and the ITT Population will only be produced on both analysis sets if there is a difference in the population groups.

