7.3 Study Subjects

7.3.1 *Disposition of Subjects*

Subject disposition will be summarized for all randomized subjects by tolperisone dose group/placebo and total tolperisone treated subjects combined. Summaries will include the number and percentage of subjects in each analysis population, subjects completing a minimum of 12 days of treatment, subjects completing the study, and those discontinuing the study early by the primary reason for discontinuation. Subject disposition will also be summarized separately for each study site.

A data listing of study disposition will be presented by treatment group, site, and subject.

7.3.2 *Protocol Deviations*

Major protocol deviations will be summarized by tolperisone dose group/placebo and for total tolperisone treated subjects combined for the ITT Population. Major protocol deviations are protocol deviations captured on-study that are deemed by the Sponsor to potentially impact the efficacy or safety conclusions of the study. Subjects with major protocol deviations will be excluded from the PP Population for analysis.

All major protocol deviations will be determined and appropriately categorized prior to database lock and prior to breaking the blind of the treatment group assignments. The number and percentage of subjects with any major protocol violations as well as the number and percentage of subjects with violations within each category will be presented. Anticipated protocol deviation categories include inclusion/exclusion criteria, investigation product, prohibited concomitant medications, visit schedule, procedures/tests, SAEs not reported/reported late, and other.

A data listing of patients with all protocol deviations will be presented by treatment group, site, subject, and date of deviation. In addition to protocol violations, a data listing of informed consent and eligibility criteria will be presented.

7.3.3 *Enrollment*

A data listing of the randomization scheme and treatment codes will be presented.

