Methods for multiple imputation (MI) for missing data may be explored for endpoints if the dropout rate is $\geq 15\%$ (60/400 subjects).

7.4.6.3 *Interim Analyses and Data Monitoring*

There are no interim analyses planned, nor is there a plan to establish a data monitoring committee for this study.

7.4.6.4 *Multicenter Studies*

This is a multicenter study, with approximately 45 sites expected to participate. Efficacy data collected from all study sites will be pooled for data analysis. The effect of study site on the efficacy analysis results may be explored post-hoc, as needed.

7.4.6.5 *Multiple Comparisons/Multiplicity*

There will be no adjustments for multiple comparisons in the efficacy analysis for this study. All of the above analyses will be conducted using two-sided tests at the $\alpha = 0.05$ level of significance.

7.4.6.6 *Use of an “Efficacy Subset” of Subjects*

The primary efficacy analysis will be performed on the ITT population; the PP population will be utilized as a sensitivity analysis for the primary endpoint and secondary endpoints, including NRS (right now, past 12 hours, past 1 hour, at rest, on movement), Subject Rating of Medication Helpfulness, Fingers to Floor Distance, Clinician’s Global Impression assessments, and Oswestry Disability Index. The PP population will exclude subjects with major protocol violations.

7.4.6.7 *Active-Control Studies Intended to Show Equivalence*

This study does not include an active-control product and is not intended to demonstrate equivalence between any two drug products.

7.4.6.8 *Examination of Subgroups*

There are no planned analyses to assess efficacy results by subgroups.

7.4.7 *Plasma Concentrations*

Plasma concentration measurements will be summarized in a separate report and is outside the scope of this SAP.

7.4.8 *Pharmacokinetic Analysis*

Pharmacokinetic analysis will be summarized in a separate report and is outside the scope of this SAP.

7.5 **Safety Evaluation**

Safety analysis will be carried out for the Safety Population, which will include all subjects who receive at least one dose of study drug. Subjects who do not complete the study, for whatever reason, will have all available data up until the time of termination included in the analysis. For safety analysis presented by study visit, the baseline value will be defined as the last value reported prior to first study drug administration. All analyses will be presented by treatment group.

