7.5.1 *Extent of Exposure*

Extent of exposure to study treatment will be summarized for the Safety Population by treatment group. The date of first and last dose is collected on the eCRF. If missing, subjects’ dosing eDiary data will be used to determine dates of first and last doses. The duration of exposure will be presented in days and calculated as the date of last dose of study drug minus the date of first dose of study drug, plus one. Duration of exposure, average dose received, and total dose received (mg) will be summarized using descriptive statistics.

Total dose received will be derived based on the number of tablets returned at the end of treatment visit and the actual dose (mg) received. Average dose will be calculated as the total

dose divided by the duration of exposure. The planned number of doses for each subject is 42 (14 days of TID dosing).

7.5.2 *Adverse Events*

Treatment-emergent adverse events (TEAEs) are defined as those adverse events (AEs) with onset on or after the first dose of study drug through 24 hours after the last dose of study drug. Existing events that worsened during this period will also be considered treatment emergent. If start time is not available, AEs with onset between the date of the first dose through the day after the date of last dose (+1 day) will be considered treatment-emergent.

Adverse events with onset greater than 24 hours (or >1 day) after the date of the last dose of study drug through the date of the follow-up visit (Visit 4/Day 28) will be considered after-treatment events.

Treatment-emergent and after-treatment AEs will be summarized by treatment group. Events reported with a partial onset date (e.g., month and year are reported but the day is missing) will be considered to be treatment-emergent if it cannot be confirmed that the event onset was prior to the first dose of study drug based on the available date entries.

Verbatim terms on case report forms will be mapped to preferred terms and system organ classes using the Medical Dictionary for Regulatory Activities (MedDRA, version 21.1).

Summaries that are displayed by system organ class and preferred terms will be ordered by descending incidence of system organ class and preferred term within each system organ class. Summaries displayed by preferred term only will be ordered by descending incidence of preferred term. Summaries of the following types will be presented:

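### SAP 7.7.2 removes Site 21 from every analysis with no safety exception, and no separate safety summary is planned for its dosed subjects

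*SAP*

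**What the plan says.** SAP 7.7.2 reports an independent audit of Site 21 in May 2019, refers to the signed inspection report, and concludes: "Site 21 subject data will be excluded from all analyses described in this SAP". It does not give the number randomized or dosed at the site, does not describe the misconduct, and does not mention safety, disposition or listings.

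The sections that define the safety and accounting outputs carry no matching change:

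- SAP 7.2, Safety Population: "All subjects who receive any amount of study drug. This population will be used for all summaries of safety data".
- SAP 7.5: "Safety analysis will be carried out for the Safety Population, which will include all subjects who receive at least one dose of study drug".
- SAP 7.5.1: "Extent of exposure to study treatment will be summarized for the Safety Population by treatment group".
- SAP 7.3.1: "Subject disposition will be summarized for all randomized subjects by tolperisone dose group/placebo and total tolperisone treated subjects combined", and also "Subject disposition will also be summarized separately for each study site".
- Protocol 17.4.3: "Safety analysis will be based on all subjects randomized who receive at least one dose of the study drug".
- Protocol synopsis, on the content of the study report: "Complete listings and summary tables for all safety information including AEs, laboratory safety data, ECG, vital signs and physical examination".

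None of the SAP sections above refers to 7.7.2.

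**The concern.** Safety and tolerability is a secondary objective of this dose-ranging study. The plan contains two rules that cannot both be followed for a dosed Site 21 subject: count everyone dosed, or count nobody from Site 21. If the second prevails, a reader of the tables cannot see how many people at that site took each dose, for how long, or whether any had a serious event. They would have to assemble it from listings.

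Finding misconduct at a site does not by itself show that nobody there was dosed or that every event recorded there is false, and 7.7.2 does not say what was found. People who may have taken the drug should be accounted for somewhere in the planned summaries, even if their data are kept apart from the rest.

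**Working it through.** **Step 1. Which outputs does 7.7.2 reach?** The plan states no figure for Site 21, so this part is a comparison of text.

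| Output | Who is counted by its own section | After 7.7.2, read literally |
|---|---|---|
| Exposure table (SAP 7.5.1) | Safety Population: everyone dosed | Site 21 absent |
| AE and SAE tables (SAP 7.5.2) | Safety Population | Site 21 absent |
| Disposition, overall and by site (SAP 7.3.1) | Everyone randomized; every site | Unclear |
| Subject listings | All enrolled subjects, as a general rule (SAP 7.1.1) | Very likely kept, not confirmed |
| Separate Site 21 safety summary | None planned | None planned |

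The exposure and AE/SAE tables are plainly analyses described in the SAP, so the exclusion covers them. Disposition is less certain. It sits under Study Subjects (7.3), outside the Efficacy (7.4) and Safety (7.5) Evaluations, and can be read as accounting rather than analysis. 7.7.2 does not settle this.

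**Step 2. Do the listings fill the gap?** Protocol 17.1 says that all efficacy and safety data are listed. SAP 7.1.1 and 7.1.2 say much the same, and 7.5.2, 7.5.3 and 7.5.4.1 plan listings of AEs, of deaths and SAEs, and of laboratory data. SAP 7.3.3 lists the randomization and treatment codes. SAP 7.4.1 lists subjects left out of the ITT or PP Population, with the reason. Against this, SAP 7.1 names listings as one of the ways in which analyses are reported, so a programmer could carry the exclusion into them. The 7.4.1 listing does not cover the Safety Population and gives no events or exposure. The weight of the text favours retention.

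**Step 3. How large could the effect be?** Inputs from the documents: 400 subjects planned, 80 per arm, so 4 x 80 = 320 on tolperisone; about 45 sites (SAP 6.1); equal allocation to five arms, stratified by site (SAP 6.3.2). Site 21's size m is an assumption. I take the average site, 400/45 = 8.9 (about 9), and a range of 5 to 30, with all subjects dosed and split evenly over the arms.

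- Tolperisone subjects omitted = m x 4/5, as a share of 320.
- Remaining per arm: n = 80 - m/5.
- 95% upper bound on an AE rate when an arm shows no events = 1 - 0.05^(1/n). With n = 80 this is 3.68%.
- Chance that the omitted tolperisone subjects include at least one case of an AE with a true rate of 1% = 1 - 0.99^(4m/5).

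| Assumed m | Omitted on tolperisone | n per arm | Upper bound, no events | Chance of at least one 1% AE omitted |
|---|---|---|---|---|
| 5 | 4 (4/320 = 1.25%) | 79 | 3.72% | 1 - 0.99^4 = 3.9% |
| 9 | 7.2 (7.2/320 = 2.25%) | 78.2 | 3.76% | 1 - 0.99^7.2 = 7.0% |
| 30 | 24 (24/320 = 7.5%) | 74 | 3.97% | 1 - 0.99^24 = 21.4% |

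Precision hardly changes. The pooled rates are not the issue; the accounting for dosed subjects is.

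**The case against.** The strongest reply is that 7.7.2 is a specific, disclosed exception that overrides general definitions. SAP section 4 says that changes from the protocol will be explained in the SAP and that the SAP is finalized before unblinding. 7.7.2 duly gives the reason and the dates. On that view the missing cross-references in 7.2 and 7.5 are editorial. This stands as far as it goes: the exclusion is open, and nothing here asks for Site 21 to be pooled. But disclosing an exclusion does not say where the excluded subjects' safety will be shown.

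A second reply is that the data may be worthless. The inspection report is not available to us, and dosing records at the site may be as unreliable as pain scores. That is a good reason to keep them out of the main tables and to attach a caveat. It is not a reason to have no summary at all.

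A third is that, at about 1.8 subjects per arm for an average site, a table by dose adds little to a listing ordered by treatment group and site. For a site of that size this is largely fair, and it keeps the point modest. The site may be larger, and its size is not stated.

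The synopsis sentence on complete safety tables should not carry much weight. It goes on to name types of data in the study report and does not address a site excluded for misconduct.

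A reader might infer that Site 21's safety data disappear from the study altogether. The documents do not support that, because every express listing rule points towards keeping them. Nor is it certain that no planned table would show the site's numbers, since the by-site disposition table may survive 7.7.2.

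**Conclusion.** The point holds as a gap in study reporting. SAP 7.7.2 has no safety exception and conflicts with SAP 7.2, SAP 7.5 and protocol 17.4.3, which remain unchanged. Applied literally, dosed Site 21 subjects are in no exposure, AE or SAE table, and no separate summary replaces them. Whether the 7.3.1 disposition tables still count them is unclear. On listings, all that is missing is a sentence of confirmation.

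The numeric effect is expected to be small: about 9 of 400 subjects and about 2% of the tolperisone subjects at an assumed average site, or 1.25% to 7.5% over an assumed 5 to 30 subjects. These figures assume that all were dosed and evenly allocated; the documents give no count for the site.

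Two stronger readings should be set aside. A reader might infer a failure of safety oversight, but protocol 16.3 still requires sites to report every SAE to the sponsor within 24 hours, whatever the cause. A reader might also infer that removing Site 21 from efficacy, or from the pooled safety tables, is itself wrong. Audit evidence of misconduct is a stated and reasonable ground for both.

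This is a cheap improvement that should be made.

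**What to change.** Amend SAP 7.7.2 to:

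1. Limit the exclusion to the efficacy analyses and the main pooled safety tables by dose.
2. State that Site 21 stays in the disposition tables, both for everyone randomized and by site, and in all subject listings.
3. Add one separate safety summary for Site 21, not pooled with other sites, giving N by arm, exposure, AEs, SAEs and deaths, with a caveat on data quality.

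Add a cross-reference to 7.7.2 in SAP 7.2 and SAP 7.5, so that the Safety Population and its exception are read together.

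The cost is a few sentences, one disposition row and one small output. The downside is that this output rests on data of doubtful reliability, hence the caveat and the separation. The efficacy exclusion and the main pooled safety tables are unaffected.
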